#### **2.4.5.4 Analyses of vital sign variables**

The summary statistics (including number, mean, median, standard deviation, minimum and maximum) of all vital signs variables (central laboratory values and changes from baseline) will be calculated for each time point or study assessment (baseline, each post-baseline time point, endpoint) by treatment arm. For parameters heart rate, systolic and diastolic blood pressures, the last on-treatment and worst on-treatment value will also be provided.

The incidence of PCSAs at any time during the TEAE period will be summarized by treatment arm irrespective of the baseline level and according to the following baseline status categories:

- Normal/missing
- Abnormal according to PCSA criterion or criteria

Listings will be provided with flags indicating the out of range values as well as PCSA values.

#### **2.4.5.5 Analyses of electrocardiogram variables**

The summary statistics (including number, mean, median, standard deviation, minimum and maximum) of all ECG variables (central laboratory values and changes from baseline) will be calculated for each time point or study assessment (baseline, each post-baseline time point, endpoints) by treatment arm.

The incidence of PCSAs at any time during the TEAE period will be summarized by treatment arm irrespective of the baseline level and according to the following baseline status categories:

- Normal/missing
- Abnormal according to PCSA criterion or criteria

Listings will be provided with flags indicating the out of range values as well as PCSA values.

#### 2.4.6 Analyses of pharmacokinetic variables

$C_{\text{trough}}$  Concentrations of SAR156597 in plasma will be described on the PK population for each time point by treatment arm and by background therapy status using descriptive statistics (number of patients, arithmetic mean (SD), geometric mean, coefficient of variation, minimum and maximum).

In a separate table,  $C_{\text{trough,av,ss}}$ ,  $C_{\text{max}}$  and  $C_{\text{Follow-up}}$  will be described on the PK population by treatment arm and background therapy status using descriptive statistics (number of patients, arithmetic mean (SD), geometric mean, coefficient of variation, minimum and maximum).

The representation of time profiles for  $C_{\text{trough}}$  concentration (mean  $\pm$  SD or Median, as appropriate) will be also provided by treatment arm and by background therapy status. Average steady state achievement will be performed by visual inspection of mean plots.

According to study results, additional plots will be prepared, as deemed necessary (eg, to explore the relationship with some safety or efficacy endpoints of interest).

The results of population PK modeling will be reported separately from the study report.

#### 2.4.7 Analyses of immunogenicity data

The following summaries will be performed on the ADA population, taking into account all samples regardless of timing in relation to injections:

- ADA results (negative, positive or inconclusive) by time point and by treatment arm
- Neutralizing status (inconclusive or positive) for positive ADA by time point and by treatment arm
- ADA titers using descriptive statistics (median, Q1, Q3, minimum and maximum) for positive ADA by time point and by treatment arm
- Number (%) of patients with pre-existing ADA and number (%) of patients with treatment-emergent ADA positive response by treatment arm
- Number (%) of patients with persistent/transient/indeterminate treatment-emergent ADA positive response by treatment arm
- Time to onset of treatment-emergent ADA positive response (in days) using descriptive statistics by treatment arm and also according to peak titer.
- Duration of ADA (in days, only for subjects with at least 2 positive ADA samples) using descriptive statistics by treatment arm.

Correlations between ADA parameters (eg, titers, treatment-emergent ADA positive status, neutralizing status) and PK, safety and/or main efficacy endpoint(s) will be explored (eg, scatter plot) according to the study results.

## 2.4.8 Analyses of Biomarker data

Biomarkers will be summarized on the Pharmacodynamics population using descriptive statistics by treatment arm and time point.

Time profile of biomarkers will be explored and link between biomarkers and treatment arm will be investigated.

Correlation between each biomarker and the main efficacy endpoint(s) will be assessed taking into account the dose and the background therapy status.

According to study results, correlation between each biomarker at baseline and  $C_{\text{trough,av,ss}}$  will be explored.

In addition, transcriptomic (mRNA) and genomic (DNA) properties will be explored.

A detailed description of the analyses will be provided apart of this SAP. The results of biomarker, transcriptomic and genomic analyses will be reported separately from the study report.

## 2.5 DATA HANDLING CONVENTIONS

### 2.5.1 General conventions

The following formulas will be used for computation of parameters.

#### *Study day*

Study day = assessment date - first IMP injection date + 1 (if assessment date  $\geq$  first IMP injection date), otherwise study day = assessment date - first IMP injection date, the day of first IMP injection being Day 1. For randomized but not treated patients, Day 1 is the day of randomization.

#### *Demographic formulas*

- Age (years) = (date of informed consent – date of birth)/365.25

#### *Disease characteristics formulas*

- Time since diagnosis of IPF (years) = (date of randomization - date of first diagnosis)/365.25
- Time since first symptoms of IPF (years) = (date of randomization - date of first IPF symptoms)/365.25
- Time from most recent date of acute exacerbation (months) = (date of randomization – date of most recent acute exacerbation)/30.4375
- Mean smoking duration:
  - for quit smokers: smoking duration = end year – start year. In case of missing end year, no imputation with analysis year.
  - for current smokers: smoking duration = analysis year - start year

### ***ECG formulas***

$$\text{Bazett (QTcB (ms))}: \text{QT (ms)} / \sqrt{60 / \text{HR (bpm)}}$$

$$\text{Fridericia (QTcF (ms))}: \text{QT (ms)} / \sqrt[3]{60 / \text{HR (bpm)}}$$

### ***Renal function formulas***

Creatinine clearance value will be derived using the equation of Cockcroft and Gault:

For Male:

$$\text{CL}_{\text{CR}} \text{ (mL/min)} = (140 - \text{age (years)}) * \text{weight (kg)} / 0.814 * \text{serumcreatinine} (\mu\text{mol} / \text{L})$$

For Female: result above multiplied by 0.85.

### ***Date of last dose of investigational medicinal product***

The date of the last dose of IMP is equal to the last date of administration reported on the IMP administration case report form page, or missing if the last administration date is unknown.

### ***Lipids variables, laboratory safety variables, hs-CRP***

For data below the lower limit of quantification (LLOQ)/limit of linearity, half of the lower limit value (i.e; LLOQ/2) will be used for quantitative analyses. For data above the upper limit of quantification (ULOQ) / limit of linearity, the upper limit value (i.e., ULOQ) will be used for quantitative analyses.

For ANCA parameter: values '<1:20' are considered as negative; other results are considered as positive.

The above rules won't be applied for the calculated LDL-C and non-HDL-C when HDL-C value is below the LLOQ. The value of LLOQ/2 for HDL-C will be used to obtain the non-HDL-C and calculated LDL-C used for quantitative analyses.

### ***ADA***

Missing baseline ADA will be considered as negative

## 2.5.2 Data handling conventions for secondary efficacy variables

### 2.5.2.1 St George Respiratory Questionnaire (SGRQ) endpoint

**Table 5 - Data handling convention for the SGRQ variable from scales**

Secondary Efficacy variable	Short Description	Data Collection	Derivation rules/Missing data handling
SGQRT: "Symptoms component" score	100 x (Sum of weights for the positive responses to questions 1 to 8) / Sum of weights for all items in Symptoms component	Self-administration questionnaire on site, entered in the database	In case of more than 2 missing items, the sum will not be calculated.  The weight for the missed item is subtracted from the total possible weight for the Symptoms component (662.5) and from the Total weight (3989.4)
SGQRT: "Activity component" score	100 x ("Sum of weights for the positive responses to questions 11 and 15) / Sum of weights for all items in Activity component	Self-administration questionnaire on site, entered in the database	In case of more than 4 missing items, the sum will not be calculated.  The weight for the missed item is subtracted from the total possible weight for the Symptoms component (1209.1) and from the Total weight (3989.4).
SGQRT: "Impacts component" score	100 x (Sum of weights for the positive responses to questions 9 to 10, 12 to 14 and 16 to 17)/ Sum of weights for all items in Impacts component	Self-administration questionnaire on site, entered in the database	In case of more than 6 missing items, the sum will not be calculated.  The weight for the missed item is subtracted from the total possible weight for the Symptoms component (2117.8) and from the Total weight (3989.4).
SGQRT total score	100 x (Sum of weights for all positive responses in the questionnaire) / Sum of total weights for the questionnaire	Self-administration questionnaire on site, entered in the database	If more than 24% of items are missing in the questionnaire, the total score will not be calculated.

It will be noted that the questionnaire requests a single response to questions 1-7, 9-10 and 17. If multiple responses are given to one of these questions then averaging the weights for the positive responses for that question are acceptable. We feel that this is a better approach than losing an entire data set and have used this technique in calculating the results used in our validation studies. (Clearly a better approach is to prevent such multiple responses occurring, but it is difficult to prevent occasional accidents).

### 2.5.3 Missing data

For categorical variables, patients with missing data are not included in calculations of percentages unless otherwise specified. When relevant, the number of patients with missing data is presented.

***Handling of computation of time since diagnosis of IPF if the date of first diagnosis is incomplete***

If the day is missing, the date is imputed to first day of the month. If the month is missing, the date is imputed to first month of the year

***Handling of computation of time since first symptoms of IPF if the date of first symptoms of IPF is incomplete***

If the day is missing, the date is imputed to first day of the month. If the month is missing, the date is imputed to first month of the year

***Handling of computation of treatment duration if investigational medicinal product end of treatment date is missing***

For the calculation of the treatment duration, the date of the last dose of IMP is equal to the date of last administration reported on the Investigational Product Administration case report form page.

The last dose intake should be clearly identified in the case report form and should not be approximated by the last returned package date.

***Handling of medication missing/partial dates***

No imputation of medication start/end dates or times will be performed. If a medication date or time is missing or partially missing and it cannot be determined whether it was taken prior or concomitantly, it will be considered a prior, concomitant, and post-treatment medication.

***Handling of adverse events with missing or partial date/time of onset***

Missing or partial AE onset dates and times will be imputed so that if the partial AE onset date/time information does not indicate that the AE started prior to treatment or after the TEAE period, the AE will be classified as treatment-emergent. No imputation of AE end dates/times will be performed. These data imputations are for categorization purpose only and will not be used in listings. No imputation is planned for date/time of AE resolution.

***Handling of adverse events when date and time of first investigational medicinal product administration is missing***

When the date and time of the first IMP administration is missing, all AEs that occurred on or after the day of randomization should be considered as TEAE. The exposure duration should be kept as missing.

The last dose intake should be clearly identified in the case report form and should not be approximated by the last returned package date.

### ***Handling of missing assessment of relationship of adverse events to investigational medicinal product***

If the assessment of the relationship to IMP is missing, then the relationship to IMP has to be assumed and the AE considered as such in the frequency tables of possibly related AE, but no imputation should be done at the data level.

### ***Handling of missing severity of adverse events***

If the severity is missing for 1 of the treatment-emergent occurrences of an AE, the maximal severity on the remaining occurrences will be considered. If the severity is missing for all the occurrences, a “missing” category will be added in the summary table.

### ***Handling of potentially clinically significant abnormalities***

If a patient has a missing baseline he will be grouped in the category “normal/missing at baseline.”

For PCSAs with 2 conditions, one based on a change from baseline value or a normal range and the other on a threshold value, with the first condition being missing, the PCSA will be based only on the second condition.

For a PCSA defined on a threshold and/or a normal range, this PCSA will be derived using this threshold if the normal range is missing; eg, for eosinophils the PCSA is  $>0.5$  GIGA/L or  $>ULN$  if  $ULN \geq 0.5$  GIGA/L. When ULN is missing, the value 0.5 should be used.

Measurements flagged as invalid by the laboratory will not be summarized or taken into account in the computation of PCSA values.

## **2.5.4 Windows for time points**

Data analyzed by time point (including efficacy, PK, BM, ADA, safety) will be summarized using the analysis windows given in [Table 6](#), [Table 7](#) and [Table 8](#). The analysis windows will be exhaustive so that data recorded at any time point (including unscheduled visits) has the potential to be summarized. These analysis windows will be applicable for all analyses (except for disease progression, all-cause mortality, IPF-related cause mortality, acute IPF exacerbations, respiratory hospitalizations, non-elective hospitalizations), and they are defined to provide more homogeneous data for time point-specific analyses. For efficacy, PK, BM, ADA, if multiple valid values of a variable exist within an analysis window, the nearest from the targeted study day will be selected. In case of ties, the maximum value will be displayed. For safety, if multiple valid values of a variable exist within an analysis window, the nearest from the targeted study day will be selected. In case of ties, the mean will be displayed.

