10.3.4 Handling of patients after permanent treatment discontinuation

Patients will be followed-up according to the study procedures as specified in this protocol up to the scheduled date of study completion, or up to recovery or stabilization of any AE to be followed-up as specified in this protocol, whichever comes last.

If possible, and after the permanent discontinuation of treatment, the patients will be assessed using the procedure normally planned for the last dosing day with the IMP (End of treatment visit/Visit 9) and then will be asked to come to the scheduled on site visits for safety monitoring and respiratory function assessment (FVC and DLCO).

All cases of permanent treatment discontinuation should be recorded by the Investigator in the appropriate pages of the e-CRF when considered as confirmed.

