### ***General common rules***

All safety analyses will be performed on the safety population as defined in [Section 2.3.2](#), unless otherwise specified, using the following common rules:

- Safety data in patients who do not belong to the safety population (eg, exposed but not randomized) will be listed separately. The baseline value is defined in [Section 2.1.4](#).
- The potentially clinically significant abnormality (PCSA) values are defined as abnormal values considered medically important by the Sponsor according to predefined criteria/thresholds based on literature review and defined by the Sponsor for clinical laboratory tests, vital signs, and ECG (PCSA version dated March 2014 [[Appendix A](#)]).
- PCSA criteria will determine which patients had at least 1 PCSA during the TEAE period, taking into account all evaluations performed during the TEAE period, including unscheduled or repeated evaluations. The number of all such patients will be the numerator for the on-treatment PCSA percentage.
- The treatment-emergent PCSA denominator by arm for a given parameter will be based on the number of patients assessed for that given parameter in the TEAE period by treatment arm on the safety population.
- For quantitative safety parameters based on central laboratory/reading measurements, descriptive statistics will be used to summarize results and change from baseline values by time point and treatment arm. Summaries will include the endpoint baseline value, the last on-treatment value and change from baseline, the worst on-treatment value and change from baseline. The last on-treatment value is commonly defined as the last value collected during the treatment period (see [Section 2.1.4](#)). The worst on-treatment value is defined as the nadir and /or the peak post-baseline during the treatment period according to the direction (minimum or maximum) of the abnormality as defined in the PCSA list.
- All measurements (scheduled or unscheduled) will be re-allocated as given in [Section 2.5.4](#) and re-allocated visits measurements will be included in the by-time point summary.
- The analysis of the safety variables will be essentially descriptive and no systematic testing is planned. Relative risks versus placebo and their 95% CIs may be provided, if relevant.

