### **2.4.5.3 Analyses of laboratory variables**

The summary statistics (including number, mean, median, standard deviation, minimum and maximum) of all laboratory variables (central laboratory values and changes from baseline) will be calculated for each time point or study assessment (baseline, each post-baseline time point, endpoint) by treatment arm. This section will be organized by biological function as specified in [Section 2.1.4.3](#) (except for pregnancy test).

For parameters glucose, monocytes, basophils, eosinophils and bicarbonate, the last on-treatment and worst on-treatment value will also be provided.

The pH parameter will be described by category:  $\leq 4.6$ ,  $>4.6$  and  $<8$ ,  $\geq 8$ .

A specific description of the following parameters will be provided at baseline by treatment arm and overall treatment groups:

- Tuberculosis information using MedDRA CMQ and the specific “Tuberculosis Assessment” eCRF page (signs and symptoms at screening (Yes, No), treated for tuberculosis in the past (Yes, No), receiving Active Anti-TB Therapy at screening (Yes, No)) and Quantiferon®-TB Gold test result (Positive, Negative, Indeterminate).
- Serology tests: hepatitis B surface antigen (Positive, Negative, Borderline), hepatitis B surface antibody (Positive, Negative, Borderline), hepatitis B core antibody (Positive, Negative, Borderline) and hepatitis C antibodies (Reactive, Unreactive, Borderline).
-  connective tissue disorders using MedDRA CMQs.

The incidence of PCSAs (list provided in [Appendix A](#)) at any time during the TEAE period will be summarized by biological function and treatment arm whatever the baseline level and according to the following baseline status categories:

- Normal/missing
- Abnormal according to PCSA criterion or criteria

For parameters for which no PCSA criteria are defined, similar table(s) using the normal range will be provided.

Listings will be provided with flags indicating the out of range values as well as PCSA values.

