**Table 6 - Analysis windows definition for efficacy**

Time point	Targeted study day	Efficacy analysis window (in study days)
Week 12	85	2 to 126
Week 24	169	127 to 210
Week 36	253	211 to 308
Week 52	365	309 to 406
Week 64	449	>406

Note: Safety and BM will follow the same analysis windows.

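### By-time-point laboratory, vital-sign and ECG summaries have no treatment-period or TEAE limit, so values taken long after the last dose enter the active-arm means and can dilute a reversible effect; the gap is clearest for ECG

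*SAP*

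**What the plan says.** **Which values enter the by-time-point rows.** SAP section 2.5.4 states: "The analysis windows will be exhaustive so that data recorded at any time point (including unscheduled visits) has the potential to be summarized". Under the general common rules of SAP section 2.4.5, scheduled and unscheduled safety measurements are assigned to windows, and "re-allocated visits measurements will be included in the by-time point summary". The windows are those for efficacy; the note under Table 6 reads "Note: Safety and BM will follow the same analysis windows". They run on study days counted from the first injection (SAP section 2.5.1), whatever the date of the last dose. Within a window one value is kept: "For safety, if multiple valid values of a variable exist within an analysis window, the nearest from the targeted study day will be selected", with the mean taken for ties.

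**What the domain sections add.** Laboratory statistics "will be calculated for each time point or study assessment (baseline, each post-baseline time point, endpoint) by treatment arm" (SAP section 2.4.5.3). ECG statistics "will be calculated for each time point or study assessment (baseline, each post-baseline time point, endpoints) by treatment arm" (SAP section 2.4.5.5). Section 2.4.5.4 does the same for vital signs. None of the three attaches an exposure condition to these rows.

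**Whether off-drug values will exist.** After permanent discontinuation, Protocol section 10.3.4 has patients complete the end-of-treatment assessments if possible; they "then will be asked to come to the scheduled on site visits for safety monitoring and respiratory function assessment (FVC and DLCO").

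**What is limited elsewhere.** SAP section 2.1.4 defines the treatment period as ending 7 days after the last dose and the TEAE period as ending 84 days after it. The general rules restrict incidence of potentially clinically significant abnormalities (PCSAs) to the TEAE period. They also plan last and worst on-treatment values, within the treatment period, for centrally measured parameters. Section 2.4.5.3 names five laboratory parameters for those rows, and section 2.4.5.4 names heart rate and the two blood pressures. Section 2.4.5.5 names none, and section 2.1.4.5 has ECGs read locally.

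**The concern.** The change from baseline by visit is where a gradual shift in a laboratory value, blood pressure or ECG interval would be seen over time. A patient who stopped months earlier still counts in the arm received, so the active-arm mean at a late visit mixes exposed patients with patients who carry almost no drug. If the effect is reversible, the mean moves towards placebo, and more so at later visits as stops accumulate. A lasting on-drug effect could then look as if it were fading.

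Stopping may also be related to the variable being summarised. Protocol section 10.3.3 lists laboratory abnormalities among the grounds for permanent discontinuation and requires abnormal ECG parameters to be rechecked before that decision. Recovered values from such patients could therefore be averaged into the active column.

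The table reader would have no sign of this, because the plan does not say which period these rows cover.

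**Working it through.** The plan gives no figure for these tables and no treatment-discontinuation rate. The nearest number is the sample-size allowance from 92 to 100 per arm, (100 − 92)/100 = 8%, which concerns dropouts rather than patients who stop treatment and keep attending.

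**1. Is the drug gone by the end of the TEAE period?** Half-life is about 11 to 15 days (Protocol section 4.2.2). The fraction remaining after 84 days is 0.5^(84/half-life):
- 11 days: 0.5^7.64 = 0.5%
- 15 days: 0.5^5.6 = 2.1%

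A post-TEAE value is effectively an unexposed one.

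**2. One patient followed through the windows.** A last dose at Week 10 falls on about Day 10 × 7 + 1 = 71. The TEAE period ends on about Day 71 + 84 = 155. The scheduled visits at Week 24 (Day 169), Week 36 (Day 253) and Week 52 (Day 365) are all post-TEAE. Each is on its window's target day, so the nearest-value rule selects it. That rule looks only at closeness to the target and does not screen for exposure.

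**3. Share of Week 52 values that are post-TEAE.** Assume a fraction d of the arm stops evenly over 364 days and everyone who stops attends Week 52. Those who stopped in the first 364 − 84 = 280 days are post-TEAE at Week 52:

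share = d × 280/364 = 0.769 d

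**4. Effect on the mean change.** Let r be the fraction of the effect that persists in post-TEAE values, and let all other values carry a constant full effect. The proportional understatement is share × (1 − r).

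| d (assumed) | post-TEAE share | r = 0 | r = 0.5 | r = 1 |
|---|---|---|---|---|
| 10% | 7.7% | 7.7% | 3.8% | 0% |
| 20% | 15.4% | 15.4% | 7.7% | 0% |
| 30% | 23.1% | 23.1% | 11.5% | 0% |

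The understatement equals the share only under full reversal. Protocol section 10.3.4 only asks patients to attend, so full return makes the share an upper figure for a given d. Values taken off drug but within 84 days are counted here as carrying full effect.

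**5. Which domains have an on-treatment counterpart?**
- Laboratory: last and worst on-treatment values under the general rule, with five parameters named in section 2.4.5.3; PCSA incidence within TEAE.
- Vital signs: last and worst named for heart rate and blood pressures, not for weight; PCSA incidence within TEAE.
- ECG: PCSA incidence within TEAE only; no last or worst summary named.

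**The case against.** Keeping all data by visit is a recognised descriptive choice, and it fits a protocol that follows patients after they stop. SAP section 2.1.7 says of biomarkers, on these same windows, that all assessments are to be described even after premature discontinuation. Safety analysis is descriptive, so no test depends on these rows. All of that stands: the fault is not that all-data rows exist, but that they are the only by-visit version and are not labelled.

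A reader might infer that every measurement from a patient who stopped is averaged in. The selection rule contradicts that: one value per patient per window is used.

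A reader might also infer that laboratory, vital-sign and ECG changes as a whole will be reported diluted. The documents do not support that either. A lasting effect would show in the last on-treatment change, a peak in the worst value, and threshold crossings in the TEAE-limited PCSA tables; TEAEs leading to discontinuation are tabulated and listed. These partly answer the concern for laboratory and vital-sign data. They do not replace the by-visit view: PCSA counts can miss a mean shift, and last and worst values give no time course.

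For ECG it could be argued that the general rule on centrally measured parameters applies, since section 2.4.5.5 refers in parentheses to central laboratory values. Section 2.1.4.5 says ECGs are evaluated locally, so this cannot be relied on.

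Finally, replacing the tables with TEAE-only rows would bring its own problem. Late rows would describe mainly patients who tolerated treatment, which can also make an effect seem to resolve. That objection holds against substitution, but not against showing both versions.

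**Conclusion.** The point holds as a minor gap in the plan. By-time-point safety rows have no treatment-period or TEAE limit, so values taken more than 84 days after the last dose will enter the active-arm means whenever patients who stopped attend, and they can dilute a reversible effect.

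About 8% to 23% of Week 52 values would be post-TEAE if 10% to 30% of an arm stops. This rests on even timing of stops over 52 weeks and full return at Week 52. The understatement of the mean change reaches that share only if the effect fully reverses; it is about half that share if half the effect persists, and nil if all of it does. The documents give neither the stopping rate nor the reversibility, so dilution is possible rather than established. The weakness is greatest for ECG, where the by-visit means have no named on-treatment counterpart.

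**What to change.** Amend SAP section 2.4.5 and the Table 6 note along these lines:

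> *By-time-point summaries of laboratory, vital-sign and ECG variables through Week 52 will be presented in two versions: values within the TEAE period only, and all values, labelled as including measurements after treatment discontinuation. Week 64 will be shown as a separate follow-up row without the TEAE restriction.*

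In SAP section 2.4.5.5, add last and worst on-treatment values and changes from baseline for ECG variables.

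Week 64 should stay unfiltered because a completer with a last dose on Day 365 leaves the TEAE period on Day 365 + 84 = 449, while the ± 2 day visit window runs to Day 451. A strict filter could drop valid follow-up values.

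The cost is one date condition, on a period already needed for the PCSA tables, and a second set of by-visit tables. The TEAE-limited late rows will describe mainly patients who stayed on treatment, which is why the all-data version should remain beside them.
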